# 6.2 **Physical examination and ECOG performance status**

Complete physical examination of the major body systems (Screening visit, Cycle 1 Days 1 and 15, Day 1 of all subsequent cycles, End of Treatment visit, and 30-day Safety Follow-up visit), height (Screening visit only), weight, vital signs (temperature [oral, axillary, or tympanic], blood pressurte, respiration rate, and pulse), and ECOG Performance Status (Appendix 2). ECOG performance status will also be evaluated during the Pre-Screening visit.

# 6.3 Complete ophthalmological examination

A complete opthalmological examination should be administered by an ophthalmologist at the Screening visit, for the first four cycles (i.e., Day 1 of Cycles 2–5), at the End of Treatment visit, at the 30-day Safety Follow-up visit, and if clinically indicated. The complete eye examination may include the following:

- visual acuity
- tonometry
- anterior segment evaluation
- retinal evaluation, which may include tests such as fluorescein angiography and optical coherence tomography

For the individual patient, the same methods of assessment should be used throughout the study.

During the study, per Investigator's discretion, a routine opthalmological examination may be performed.

Patients who develop ocular symptoms or changes in visual acuity while on the study should be referred to the ophthalmologist for a complete opthalmological examination.

## 6.4 12-lead electrocardiogram

A standard, triplicate, 12-lead ECG must be performed using the pre-programmed device provided by the Sponsor:

- at the Screening visit
- on Day 1 and Day 15 of Cycle 1 (pre-dose, and approximately 6–8 hours after the dosing)
- on Day 1 of Cycle 2 (pre-dose)
- on Day 1 of Cycle 3 (pre-dose, and approximately 6–8 hours after the dosing)
- on Day 1 of Cycle 4 and all subsequent cycles (pre-dose); and
- at the End of Treatment visit

Measurements should be separated by  $\sim 1$  min and be taken within a 5 min time window. The on-treatment ECGs should be performed as close as possible to the corresponding PK blood collection time point during those visits; if possible, ECG should be measured first, and then blood collected for PK within 5–10 minutes. Additional ECGs may be conducted if clinically indicated.

ECGs must always be recorded after at least 5 min rest and while the patient is in a supine or semi-supine position. ECGs must be assessed, and the printouts signed and dated, by the Investigator or his/her designee.

All ECGs are to be transmitted to a central ECG laboratory for evaluation, including QTc assessment.

# 6.5 Clinical laboratory tests

Safety laboratory determinations will include hematology, blood chemistry, liver function tests, and coagulation tests at the Screening visit (within 1 week prior to dosing), Cycle 1 Days 1 and 15, Day 1 of all subsequent cycles, the End of Treatment visit, and the 30-day Safety Follow-up visit. If clinically indicated, some or all of these tests may be repeated on other study days. All laboratory tests will be performed at a central laboratory designated by the Sponsor.

- Hematology: complete blood count (CBC) including hemoglobin, hematocrit, white blood cell count (WBC) with 5-part differential, red blood cell (RBC) count, and platelet count
- Blood chemistry: albumin, bicarbonate, blood urea nitrogen (BUN), calcium, chloride, creatinine, glucose, magnesium, phosphate, potassium, total protein, sodium, and uric acid
  - Creatinine clearance as calculated by the Cockcroft-Gault equation (at the Screening visit only)
  - 25-hydroxy vitamin D and 1,25-dihydroxy vitamin D (at C1D1, C3D1, C5D1, and the End of Treatment visit only),

- Liver function tests (LFT): ALT, AST, ALP, total and direct bilirubin, lactate dehydrogenase (LDH)
- Coagulation tests: prothrombin time (PT), INR, and partial prothrombin time (PTT) (at the Screening and End of Treatment visits and if clinically indicated)
- Serum pregnancy test: for women of child-producing potential at the Screening visit (within 72 hours prior to dosing), and End of Treatment visit. In addition, serum- or urine pregnancy testing will be performed monthly (on Day 1 of each treatment cycle) while the patient receives study treatment, at the 30-day Safety Follow-up visit, and monthly until 120 days after the last administration of study drug. Pregnancy testing after the End of Treatment may be performed at the patient's local gynecologist to reduce the burden related to study visits at the site, but must be communicated to the study investigator.

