#### 7.7.2 Prohibited treatment / treatment to be avoided or used with caution

The following treatments are not allowed during the study:

- Any concurrent anti-cancer therapy including chemotherapy, radiotherapy, hormonal, targeted therapy, or immunotherapy
  - Palliative radiotherapy for non-hepatic local pain-control may be allowed, provided the patient does not meet criteria of progressive disease and treated lesions will not be included in the target/non-target lesion assessment
- Other investigational agents
- Immunosuppressive therapies, including systemic corticosteroids (except up to a 25 mg/day prednisone-equivalent dose or when used intermittently in an antiemetic regimen, for CNS metastases management or as premedication for imaging studies)

The following treatments should be avoided, if possible, or used with caution during the study:

- Derazantinib may inhibit CYP2C8, CYP1A2, or CYP2D6 metabolism, hence coadministration of derazantinib with drugs known to be substrates of CYP2C8, CYP1A2, or CYP2D6 should be avoided or used with caution (see Appendix 4)
- Derazantinib may be a substrate and inhibitor of human P-glycoprotein (P-gp), therefore co-administration of derazantinib with drugs known to be P-gp substrates with narrow therapeutic index should be avoided or used with caution (see Appendix 5)
- Drugs with known liver toxicity, e.g., clotrimazole, should be avoided or used with caution; if such drugs need to be administered, LFT should be done every 4–5 days during the drugs' co-administration
- Drugs with the potential to prolong QT interval (see Appendix 9)

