#### 3.1.3 Visit Windows

All data will be tabulated per the evaluation visit as recorded on the electronic case report form, even if the assessment is outside of the visit window. With the exception of the baseline definition, unless otherwise stated in the analysis sections below, unscheduled visits will only be included in data listings.

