#### 3.2.8.2 Laboratory Variables

Local laboratory results will only be listed.

Central laboratory results will be summarized with descriptive statistics at each scheduled time and for the change from baseline. Repeated or unscheduled tests will not be summarized for each scheduled visit (with the exception of baseline which may include unscheduled visits). Baseline values and values at each visit for each laboratory parameter collected be descriptively summarized and plotted over time using a boxplot.

Laboratory data will also be summarized using shift tables where appropriate. Each patient's continuous laboratory safety parameter values will be flagged as "low", "normal", "high" or "missing" relative to the normal ranges. Each patient's categorical laboratory safety parameter values will be flagged as "abnormal" or "normal". This categorical data will be summarized in shift tables comparing the minimum post-baseline value, maximum post-baseline value and all other relevant post-baseline visits with those at the baseline visit. Note that minimum post-baseline will only be displayed in the instances where there is a range with lower limit of normal (LLN) >0. For parameters that have gradings for both low and high values, low and high will be summarized separately.

In the shifts of low values, any high values will be classified as normal and the worst low grade will be summarized. And in the shifts of high values, any low values will be classified as normal and the worst high grade will be summarized.

In addition, CTCAE grade and hyperphosphatemia grade will be summarized. Shift tables of grade from baseline to maximum or minimum on-treatment as applicable will be produced.

Since hyperphosphatemia is not defined by CTCAE v. 4.03, as per protocol hyperphosphatemia is defined as:

Grade 1: > upper limit of normal (ULN) to < 7.0 mg/dL (<2.26 mmol/L)

Grade 2: Non-invasive intervention required (e.g., withhold drug or modify dose) or between 7.0 - 9.0 mg/dL (2.26 - 2.90 mmol/L)

Grade 3: Severe or medically significant, but not immediately life threatening, or > 9.0 - 10.0 mg/dL (> 2.90 - 3.23 mmol/L)

Grade 4: Life-threatening consequences, urgent intervention indicated e.g., dialysis, or > 10.0 mg/dL (> 3.23 mmol/L)

Central and local laboratory results will be included in by-patient listings and will include CTCAE grade and hyperphosphatemia grade at each visit, as well as change from baseline at each visit.

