# Hy's law

Patients who have elevated alanine aminotransferase (ALT), aspartate aminotransferase (AST), and total bilirubin post baseline will be summarized descriptively as follows and Hy's law cases identified.

- ALT and AST: > 3x ULN, > 5x ULN, > 10x ULN, > 20x ULN
- Total bilirubin >2x ULN
- ALT or AST: > 3x ULN and Total bilirubin >2x ULN

Plots of ALT and AST vs. Total bilirubin by module will also be produced with reference lines at 3×ULN for ALT, AST, and 2×ULN for total bilirubin. In each plot, peak total bilirubin x ULN will be on the vertical axis and peak ALT or AST x ULN will be on the horizontal axis.

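### The SAP default sends unscheduled laboratory results to listings and excepts only baseline, so as written the worst-value and Hy's law summaries can miss between-visit extremes

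*Protocol*

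**What the plan says.** **The default.** SAP 3.1.3 tabulates data by the visit recorded on the eCRF and then, baseline aside, states: "unless otherwise stated in the analysis sections below, unscheduled visits will only be included in data listings".

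**The laboratory section.** SAP 3.2.8.2 keeps local results to listings. For central results it says: "Repeated or unscheduled tests will not be summarized for each scheduled visit (with the exception of baseline which may include unscheduled visits". It then plans three summaries of extremes:

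- Low/normal/high categories, "summarized in shift tables comparing the minimum post-baseline value, maximum post-baseline value and all other relevant post-baseline visits". The minimum is shown only where the lower limit of normal is above zero.
- Toxicity grades: "Shift tables of grade from baseline to maximum or minimum on-treatment as applicable will be produced".
- Hy's law: "Patients who have elevated alanine aminotransferase (ALT), aspartate aminotransferase (AST), and total bilirubin post baseline will be summarized descriptively". The categories use multiples of ULN, and the accompanying plots use peak values.

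**Tests that the protocol itself directs between visits.** Protocol 7.7.2 says of drugs with known liver toxicity: "if such drugs need to be administered, LFT should be done every 4–5 days". Table 5 in Protocol 7.3.2 calls for weekly phosphate reassessment while derazantinib is withheld. Protocol 6.5 allows any safety test to be repeated on other days when clinically indicated.

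**Coagulation.** The opening sentence of Protocol 6.5 puts "coagulation tests at the Screening visit (within 1 week prior to dosing), Cycle 1 Days 1 and 15, Day 1 of all subsequent cycles", and goes on to End of Treatment and the 30-day visit. The bullet lower down gives "prothrombin time (PT), INR, and partial prothrombin time (PTT) (at the Screening and End of Treatment visits and if clinically indicated". Appendix 1 has one row for clinical blood tests, and its footnote refers back to 6.5.

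**The concern.** A table headed maximum post-baseline, or worst on-treatment grade, is read as the worst value that the patient had. Extra tests are usually ordered because something is wrong or a risk has been added, so they are a likely place for the extreme to occur. If they are dropped by default, the table understates toxicity without saying so. The analyte that matters most is liver enzymes: Protocol 7.8 classes increased transaminases as an important identified risk, and the between-visit liver tests in 7.7.2 are aimed at patients with added hepatotoxic exposure. Two programmers working from the same final SAP could also build different tables.

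**Working it through.** The plan states no figure on this point, so there is none to reproduce. The check is mainly textual.

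**Step 1: what the default requires.** SAP 3.1.3 gives way only where an analysis section states otherwise. So the question for each summary is whether 3.2.8.2 makes such a statement.

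| Summary in SAP 3.2.8.2 | Statement on unscheduled results | Result under the 3.1.3 default |
|---|---|---|
| Baseline | May include them | Included |
| By-visit values and changes | Excluded | Excluded |
| Minimum/maximum post-baseline shifts | None | Listings only |
| Grade shift to on-treatment maximum/minimum | None | Listings only |
| Hy's law categories | None (plots refer to peak values) | Listings only |

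The default covers every analyte; it is not a rule about any one test.

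**Step 2: whether protocol-directed tests fall off schedule.** From Cycle 2 on, Protocol 6.5 schedules one liver panel per 28-day cycle, on Day 1. Suppose hepatotoxic co-medication lasts a whole cycle:

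- Every 4 days: Days 5, 9, 13, 17, 21, 25 = 6 tests before the next Day 1 (Day 29).
- Every 5 days: Days 6, 11, 16, 21, 26 = 5 tests, or 4 if Day 26 is taken as the next visit under the ±3-day window.

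Weekly phosphate during a hold adds Days 8, 15 and 22 = 3 tests. Only results recorded as unscheduled are affected; a test entered under a scheduled visit is tabulated there.

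**Step 3: consequence for one patient.** Suppose ALT exceeds 3×ULN and total bilirubin exceeds 2×ULN only at an unscheduled central draw, and both are lower at the visits on either side. Under the default this patient appears in the by-patient listing but not in the combined category that the Hy's law section defines. If all post-baseline values were used, the patient would be counted.

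**Step 4: the coagulation wording.** Let n be the number of cycles started, with Cycle 1 Day 1 bloods taken before dosing. Scheduled post-baseline values are:

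- Opening sentence: C1D15 (1) + later Day 1 visits (n − 1) + End of Treatment (1) + 30-day visit (1) = n + 2. For n = 1, 2 and 8 this is 3, 4 and 10.
- Bullet: End of Treatment only = 1, whatever n is.

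Counted by calendar time, one to eight months on treatment means 2 to 9 cycles started, so 4 to 11 values against 1. If the bullet governs, PT, INR and PTT depend more on unscheduled results than any other analyte. If the opening sentence governs, they are no more exposed than hematology, chemistry or liver tests.

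**The case against.** The best defence is that the SAP does not clearly exclude these values. SAP 3.1.3 sits under visit windows. The laboratory section restates the rule more narrowly, as one about summaries for each scheduled visit, and the same sentence recurs in 3.2.8.3, where only by-visit summaries of vital signs are planned. The shift-table text names the minimum and maximum separately from the other visits, and the Hy's law plots use peak values with no limit on visits. On that reading, extremes already draw on all post-baseline results. This has force: a reader might infer that the SAP flatly removes unscheduled values, and that is too strong. But the narrower wording is not the express statement that 3.1.3 asks for, so the default still applies on the text.

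Three further objections stand in part.

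- **Other routes to the same information.** Listings carry every central and local result with its CTCAE grade. Protocol 8.2 has investigators assess adverse events at non-scheduled visits, including by reviewing laboratory results. SAP 3.2.8.1 plans special-interest TEAE tables for transaminase elevations and hyperphosphatemia, and SAP 3.2.6 summarizes reasons for dose changes. These offset the gap only partly, because adverse event entry rests on investigator judgement while the shift table is the systematic laboratory summary.
- **Local testing.** Protocol 6.5 makes testing central, but the SAP provides for local results and only lists them. Any between-visit test run locally stays in listings under that separate rule.
- **Coagulation.** Other sub-items in 6.5, such as creatinine clearance and vitamin D, narrow the general schedule, and the clinically indicated clause would add little if coagulation were already tested at every visit. The bullet is most naturally the specific rule. Against that, those other items say only, the coagulation bullet does not, and the opening sentence names coagulation. The mismatch is real but editorial.

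**Conclusion.** The point holds as a gap in the SAP's specification. Followed as written, unscheduled central results do not enter the minimum, maximum and worst-grade summaries or the Hy's law categories; the text is arguable but supplies no override. It is worth correcting because the analytes include transaminases and the correction is cheap. It touches descriptive safety summaries only: no efficacy result, error rate or baseline value changes.

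The effect cannot be sized. The documents do not give the frequency of unscheduled tests, the number of patients on hepatotoxic co-medication or anticoagulants, or which laboratory would run the extra tests. From Step 2 a reader might infer that most of the evidence is lost: 6 of 7 draws (86%) or 5 of 6 (83%) for liver tests, and 3 of 4 (75%) for phosphate. Those are shares of draws while a trigger lasts a whole cycle, not shares of missed maxima. Phosphate rechecks in particular follow a recorded high value with drug withheld, so they are less likely to hold the maximum.

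A reader might also infer that INR needs testing every cycle in anticoagulated patients, since criterion 8 admits INR up to 3 on warfarin or heparin, Appendix 4 lists warfarin as a CYP1A2 substrate, and 7.7.2 advises avoidance or caution with such substrates. The documents give no evidence that derazantinib raises INR, and clinically indicated testing is already allowed. They do not support an amendment at up to about 70 sites for that purpose.

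**What to change.** Add to SAP 3.2.8.2, for all laboratory parameters including coagulation:

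> Unscheduled and repeat central-laboratory results count toward the minimum, maximum and worst-grade post-baseline summaries and toward the Hy's law categories. By-visit summaries use scheduled visits only. Local results remain listing-only.

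The cost is one sentence and minor programming before database lock, with no patient burden. The documents do not say whether the database has been locked; SAP 2.3 places lock after this plan. Protocol Section 10 requires changes to the planned methods to be described and justified in the clinical study report, so the change should be noted there.

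At the next protocol amendment made for other reasons, state one coagulation schedule in 6.5. If the bullet is meant, remove coagulation from the opening sentence. This does not justify an amendment of its own.

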# 6.6 Pharmacokinetic assessments

Blood samples will be taken to determine the PopPK parameters of derazantinib. Exploratory assessments of metabolites of derazantinib may also be investigated from the same samples.

Time windows are allowed for sample collection as detailed in Appendix 3.

## 6.6.1 Sparse PK sampling (all patients)

On Cycle 1 Day 1 and Day 15, and on Cycle 3 Day 1, PK plasma samples will be collected pre-dose and between 6 and 8 hours after the daily dose of derazantinib. On Day 1 of Cycles 2 and 4, PK plasma samples will be collected at pre-dose (see Appendix 3). The blood sampling date and time and the time of derazantinib administration on the day of the PK blood draw and on the day prior to the PK blood draw should be recorded on the electronic case report form (eCRF).

#### 6.6.2 Rich PK sampling (additional consent required)

In the PK/biomarker subgroup (up to 20 patients), on Day 1 of Cycle 1 and Cycle 2, serial PK plasma samples will be collected pre-dose, and 1, 2, 4, 6, 8, 10, 12, and 24 h after the daily dose of derazantinib (immediately prior to the next dose); the 10 and 12 h time-points are optional. On Day 15 of Cycle 1 and Day 1 of Cycle 3, PK plasma samples will be collected pre-dose and between 6 and 8 hours after the daily dose of derazantinib. On Day 1 of Cycle 4, PK plasma samples will be collected at pre-dose (see Appendix 3). Patients will be asked for an additional consent to participate in these assessments.

# 6.6.3 Urinary PK sampling (additional consent required)

Patients who undergo urinary PK sampling should also undergo rich blood PK sampling. In the PK/biomarker subgroup (up to 20 patients), urine will be collected over a 24 h interval on Day 1 of Cycle 2 to determine renal excretion of derazantinib. Exploratory assessments of metabolites of derazantinib may also be investigated from the PK urine samples (see Appendix 3). Patients will be asked for an additional consent to participate in these assessments.

#### 6.7 Pharmacodynamic assessments

The goal of PD assessments is to identify additional markers to allow a better prediction of response to derazantinib or other cancer treatments, and to evaluate the tumoral and serum-or plasma-based PD response in patients treated with derazantinib.

Blood samples for PD assessments will be collected for serum tumor markers (CA19.9, CA125, CEA), biomarkers (FGF19, FGF21, FGF23), and ctDNA prior to the first dose on Day 1 of Cycle 1, and on Day 1 of every 8 weeks (every two cycles) for the first six cycles (C3D1, C5D1, C7D1), once every 12 weeks (three cycles) thereafter (C10D1, C13D1, etc.), and at the End of Treatment visit. Blood samples for serum tumor markers will be collected for all enrolled patients. Blood samples for biomarkers and ctDNA will be collected only from patients enrolled after completion of the interim analysis.

Archival tumor samples will be obtained for all patients to enable additional molecular analyses with regard to the identified GAs and markers predictive of response at the laboratories selected by the Sponsor (see Section 6.8).

The planned analyses include, but are not limited to, biomarkers identifying additional markers to allow a better prediction of response to derazantinib or other cancer treatments, biomarkers representing further MAPK (RAS/RAF/MEK/ERK), PI3K/AKT, and JAK/STAT pathways, biomarkers indicating PI3K, PTEN, EGFR, MET and ERB3 signaling, and biomarkers demonstrating phosphorylation status of phospho-S6, phosphor-STAT, phospho-AKT, phospho-MEK, phospho-ERK, and RNA-expression of proteins activated by the MAPK-pathway, such as SPRY2 and DUSP6.

All collected samples will be evaluated in batches either during or after the end of the study. All testing will be performed at a laboratory designated by the Sponsor. Samples remaining from PD analyses may be used to supplement diagnostic analysis batches, and vice versa.

# 6.8 Tumor tissue testing for confirmation of patient eligibility

To be eligible for enrollment, the patient must either test positive for *FGFR2* fusion (Substudy 1), or test positive for *FGFR2* mutation/amplification (Substudy 2).

#### 6.8.1 FISH testing

FISH testing will be the primary method to confirm *FGFR2* fusions in Substudy 1.

If the *FGFR2* fusion is identified by a laboratory other than the Sponsor's central laboratory, then archival and/or recent tissue biopsy samples or a tissue block suitable for biomarker analysis must be available for confirmatory testing using the break-apart FISH test by the Sponsor's central laboratory (ARUP laboratories; Salt Lake City, USA). These samples should be sent to the central laboratory as early as possible, and no later than 4 weeks after the patient received the first dose of derazantinib.

Table 1 describes the testing approach depending on *FGFR2* GA status and available results from local molecular pre-screening. Central laboratory FISH testing using the break-apart FISH test should be performed on all tissue samples from potentially eligible patients with iCCA for whom:

- No local pre-screening results (by FISH or NGS) are available, or
- Where pre-screening results (by FISH or NGS) have identified an *FGFR2* fusion and the patient is planned for study inclusion or has already been included in the study

Tissue from Substudy 1 patients with a negative result from a test other than the central laboratory FISH test designated by the Sponsor may also be submitted to central confirmatory FISH testing. If the central FISH testing is positive, the patient may be enrolled in the study.

Local pre-screening result	Confirmatory testing approach	Main testing purpose/comment	
No local testing performed	Central FISH (mandatory)	Detect eligible FGFR2 fusion status	
Local FISH test positive for	Central FISH (mandatory)	Confirm or exclude FGFR2 fusion	
FGFR2 fusion	NGS (optional)	Characterize FGFR2 fusion	
Local NGS test positive for FGFR2 fusion	Central FISH (mandatory)	Confirm FGFR2 fusion	
Local NGS test negative for FGFR2 fusion	Central FISH (optional, depending on tissue availability)	Detect eligible FGFR2 fusion status	
Tumor tissue requirements:Central FISH: $\geq$ 6 consecutive, unstained, $5 \pm 1 \ \mu m$ thick sections placed on positively charged slides.NGS testing: $\geq$ 10 consecutive, unstained, $5 \pm 1 \ \mu m$ thick sections placed on positively charged slides, and one H&E slide.			

 Table 1
 Substudy 1: Overview of genetic testing for FGFR2 fusions

Central FISH testing will be performed on formalin-fixed paraffin-embedded (FFPE) primary liver cancer specimens, including iCCA tissue samples. A minimum of 6 consecutive, unstained,  $5 \pm 1 \mu m$  thick sections placed on positively charged slides are required. Archived tissue specimens may be submitted if they meet the requirements outlined in the Laboratory Manual.

Archival tumor samples will be obtained for all patients to enable additional molecular analyses with regard to the identified GAs and markers predictive of response at the laboratories selected by the Sponsor.

